4.2 Exclusion Criteria

All subjects meeting any of the following exclusion criteria at time of enrollment will be excluded from study participation.

4.2.1 Symptomatic, extensive-stage KS (T1 by the ACTG staging system; T1 includes ulceration or edema from KS, raised or non-hard palate oral lesions, or any visceral

involvement) requiring urgent treatment, to avoid potential rituximab-induced KS worsening.

- 4.2.2** Previous rituximab use for MCD.
- 4.2.3** Second active malignancy requiring systemic therapy.
- 4.2.4** If HIV negative and a) hepatitis B virus surface antigen positive or unless on tenofovir or lamivudine. All HIV-infected patients must be on tenofovir or lamivudine as part of the inclusion criteria.
- 4.2.5** Active infection requiring systemic therapy.
- 4.2.6** Treatment with any investigational drug within 28 days prior to registration.
- 4.2.7** More than 7 days of corticosteroids immediately prior to enrollment. If subject is taking corticosteroids for more than 7 days, they require a 7 day washout period before enrollment.
- 4.2.8** Bilirubin >3 mg/dL.
- 4.2.9** Creatinine clearance <30 ml/min by Cockcroft-Gault formula.
- 4.2.10** ECOG performance status >3.
- 4.2.11** Pregnant or breastfeeding (NOTE: breast milk cannot be stored for future use while the mother is being treated on study).

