5.3 Toxities and Dosing Delays/Dose Modifications

Any patient who receives treatment on this protocol will be evaluable for toxicity. Each patient will be assessed periodically for the development of any toxicity according to the Time and Events table (Section 8.1). Toxicity will be assessed according to the National Cancer Institute (NCI) CTCAE, v5.0. Dose adjustments should be made according to the system showing the greatest degree of toxicity. See **Tables 2-4** below for recommended dose delays/dose modifications.

Assigning cause of death is often difficult in Malawi because diagnostic capabilities are limited and deaths frequently occur outside of health facilities. To address this challenge, two senior non-study clinicians will be enlisted to review all study data for deceased patients and assign cause of death as either likely treatment-related, MCD-related, related to another cause, or unable to determine. In the event of discordant conclusions, a third senior clinician will serve as a tiebreaker.

Table 2: Hematological toxicity dose reductions		
ANC	Platelets	Action
≥ 0.5 x 10 ³ /µL	≥ 50 x 10 ³ /µL	None.

$< 0.5 \times 10^3/\mu\text{L}$	$< 50 \times 10^3/\mu\text{L}$	
FIRST EPISODE: Hold current etoposide dose until ANC $\geq 0.5 \times 10^3/\mu\text{L}$ and platelets $\geq 50 \times 10^3/\mu\text{L}$. Restart next treatment at 75 mg/m^2. Do NOT hold or reduce rituximab dose.
 
SECOND EPISODE: Hold current etoposide dose until ANC $\geq 0.5 \times 10^3/\mu\text{L}$ and platelets $\geq 50 \times 10^3/\mu\text{L}$. Restart next treatment at 50 mg/m^2. Do NOT hold or reduce rituximab dose.
 
Goal is to replace doses and complete full course of four doses of both etoposide and rituximab.

---------------------------------	--------------------------------	--

Table 3: Non-hematological toxicity dose reductions for rituximab	
NCI CTC Grade	
0-2	No change from original dose.
3-4	Wait until resolved to \leq Grade 2, no dose reduction.
Second episode of Grade 3 or 4 toxicity	Hold until resolved to \leq Grade 2, no dose reduction.
Third episode of Grade 3 or 4 toxicity	Remove subject from trial

Table 4: Hepatic and renal dysfunction dose adjustment for etoposide	
Event	Action
Renal dysfunction	
Cr clearance $>50 \text{ ml/min}$	None
Cr clearance 15-50 ml/min	Decrease dose to 75 mg/m^2
Cr clearance $<15 \text{ ml/min}$	Decrease dose to 50 mg/m^2
Hepatic dysfunction	
Bilirubin $<1.5 \text{ mg/dL}$	None

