5.7 Duration of Therapy

In the absence of treatment delays due to AEs, treatment may continue for **4 weekly doses** or until one or more of the following occur:

- Disease progression
- Inter-current illness that prevents further administration of treatment
- Unacceptable AE(s)
- Pregnancy
- Subject decides to withdraw from study treatment
- General or specific changes in the subject's condition render the subject unacceptable for further treatment in the judgment of the investigator

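### Table 2's fixed etoposide restart doses conflict with Table 4: a patient already on 75 mg/m² gets no reduction at the first severe cytopenia, and, read literally, a patient on 50 would be raised to 75

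*Combined protocol and SAP*

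**What the plan says.** Only high-risk patients receive etoposide: 100 mg/m² on days 1, 8, 15 and 22 (sections 5.1 and 5.2).

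Section 5.3 adjusts that dose in two places.

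- **Blood counts.** The table is headed "Table 2: Hematological toxicity dose reductions". When ANC is below 0.5 or platelets are below 50 (×10³/µL), etoposide is held until both recover. After the first episode the instruction is "Restart next treatment at 75" mg/m²; after the second it is "Restart next treatment at 50" mg/m². The same cell states the aim of making up doses so that all four are given.
- **Kidney and liver (Table 4).** The row "Cr clearance 15-50 ml/min" sets etoposide at 75 mg/m². Bilirubin 1.5–3.0 mg/dL sets it at 50, as does clearance below 15.

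Exclusion 4.2.9 is "Creatinine clearance <30 ml/min by Cockcroft-Gault formula", so patients with clearance 30–50 can enrol. Exclusion 4.2.8 bars bilirubin above 3 mg/dL, so patients at 1.5–3.0 can enrol too.

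The one sentence that links the tables is "Dose adjustments should be made according to the system showing the greatest degree of toxicity".

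**The concern.** A restart dose written as a fixed amount is a reduction only for a patient who was on more than that amount. Table 2 fits a patient on 100. It does not fit a patient whom Table 4 has already moved to 75 or 50.

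Sections 1.4 and 6.2.1 say that etoposide should be reduced in proportion to the loss of creatinine clearance. The renal cut to 75 therefore offsets slower elimination and is not an advance response to marrow toxicity. A patient who reaches ANC <0.5 on 75 has had a severe cytopenia at that adjusted dose, and section 6.2.1 describes myelosuppression as dose related.

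At stake is the safety of an individual patient with impaired clearance or raised bilirubin, at a site where G-CSF is not routinely available (section 5.4.1).

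**Working it through.** There is no power or error-rate figure to reproduce. The check follows each starting dose through both tables and then adds up the doses.

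**Assumptions about the text.** Table 4 sets the dose from the first treatment; it does not say so outright, but its wording and the clearance floor of 30 support that. Either count below its threshold triggers Table 2.

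**Dose at start, after the first episode, after the second (mg/m²)**

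| Patient | Table 2 taken literally | Lower of Tables 2 and 4 |
|---|---|---|
| Clearance >50, bilirubin <1.5 | 100, 75, 50 | 100, 75, 50 |
| Clearance 30–50 at entry (15–50 on study) | 75, 75, 50 | 75, 75, 50 |
| Bilirubin 1.5–3.0, clearance >50 | 50, 75, 50 | 50, 50, 50 |

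For the patient on 75 the readings agree, so it does not matter which table governs. For the patient on 50 they differ. The linking sentence tells the site to follow the worst-affected system. After a severe cytopenia that is most naturally the marrow, which points to Table 2 and a restart at 75.

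**Total over four doses, patient on 75, one episode.** As written: 4 × 75 = 300. With a one-level step-down:

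- after dose 1: 75 + 50 + 50 + 50 = 225 (−75/300 = −25%)
- after dose 2: 75 + 75 + 50 + 50 = 250 (−50/300 = −16.7%)
- after dose 3: 75 + 75 + 75 + 50 = 275 (−25/300 = −8.3%)
- after dose 4: 300 (no change)

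Section 6.2.1 puts the granulocyte nadir 7–14 days and the platelet nadir 9–16 days after a dose. After dose 1 on day 1 these fall on days 8–15 and 10–17. The −25% case needs counts already below threshold at the day 8 visit, so the −16.7% case (day 15 visit) is at least as plausible.

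**Patient on 75, two episodes**

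- after doses 1 and 2: 75 + 75 + 50 + 50 = 250 as written, 225 with the step-down (−10.0%)
- after doses 1 and 3: 75 + 75 + 75 + 50 = 275, against 225 (−18.2%)
- after doses 2 and 3: 275, against 75 + 75 + 50 + 50 = 250 (−9.1%)

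**Patient on 50, one episode after dose 1.** Literal reading: 50 + 75 + 75 + 75 = 275. With a cap: 4 × 50 = 200. The literal total is 75/200 = 37.5% higher.

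**Patient on 100, one episode after dose 1.** 100 + 75 + 75 + 75 = 325, as written and with the step-down.

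**How many patients on 75?** The documents do not say. Assume 30–70% are high-risk, 5–20% of those have clearance 30–50, and 3–37% of those have a qualifying cytopenia. The last range comes from Table 6: platelets <50,000 in 1–20% and WBC <1,000 in 3–17%, from complete overlap (3%) to none (20 + 17 = 37%). WBC only stands in for ANC, for which Table 6 gives no rate.

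- low: 27 × 0.30 × 0.05 × 0.03 = 0.01
- middle: 27 × 0.50 × 0.10 × 0.15 = 0.20
- high: 27 × 0.70 × 0.20 × 0.37 = 1.40

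The documents give no basis for a similar count of patients on 50.

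**The case against.** **The tables are advisory.** Section 5.3 points to them as "below for recommended dose delays/dose modifications", and section 5.7 lets treatment stop for intolerable adverse events. That stands, but the recommendation itself names 75, and stopping is blunter than going to 50.

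**There is already a response to the first episode.** A reader might infer that the plan does nothing. The documents do not support that: etoposide is held until counts recover, a second episode does bring 50, and supportive care covers platelet transfusion (section 5.4.2) and febrile neutropenia (Appendix A). Section 6.2.1 adds that marrow recovery is usually complete by day 20, with no cumulative toxicity reported. Only the dose step is missing.

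**Stepping down early uses up the only step.** This is the strongest objection, and it stands. With the change the sequence is 75, 50, 50, so the second episode brings no cut, and neither table goes below 50 mg/m². Whether to use the step early or late is a clinical judgement.

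**Less etoposide may cost efficacy.** It is given to lower early death in high-risk patients (section 1.3), Table 2 aims for a full course, and low platelets can be part of the MCD flare itself (criterion 4.1.7). All true. Table 2 already accepts this trade-off for patients on 100, and the protocol gives no reason to treat those on 75 differently.

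**A sensible clinician would not raise a patient from 50 to 75.** Probably so, and the table heading supports that view. But no sentence in section 5.3 makes the Table 4 dose a ceiling, and the linking sentence points the other way. Nor do the documents show that any patient would in practice be raised.

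**Conclusion.** The point holds as a minor one. For a patient on 75, the rule as written gives no reduction at the first severe cytopenia. For a patient on 50, its literal reading gives an increase. No other text supplies the missing step or a ceiling. Confidence is high for the dose sequences and only moderate for clinical benefit, because nothing in the documents shows harm from resuming 75 after counts recover.

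For a patient on 75 with one episode before the last dose, the difference is 25 to 75 mg/m² over the course. Probably zero or one patient on 75 is affected. That range is wide because the high-risk and clearance shares are assumed, and Table 6 pools oral and intravenous use, several schedules and many cancers.

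A reader might infer that the trial's safety conclusion is at risk. The documents do not support that. The primary endpoint counts non-hematologic Grade ≥3 events and treatment-related deaths, not cytopenias, and a handful of mg/m² in so few patients would not alter what the trial concludes.

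**What to change.** Keep the hold rule and reword the restart in Table 2:

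*Restart etoposide one level below the dose that preceded the episode (100 to 75, 75 to 50 mg/m²). The restart dose is never above the dose the patient was receiving or the dose Table 4 currently allows.*

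Add a line saying whether etoposide continues at 50 or stops after a recurrence at 50, since the new rule leaves no further step there.

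This is a wording change in one amendment, with no added patients, visits or tests. Patients on 100 follow the same steps as now. The cap has no real downside and can be adopted outright. The step-down gives up some etoposide in high-risk patients, so the sponsor's clinicians should confirm it.

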5.4 Concomitant Medications/Treatments/Supportive Care Allowed

5.4.1 Hematopoietic growth factors

- Recombinant granulocyte colony-stimulating factor (G-CSF) and recombinant erythropoietin will not be routinely available, as is typical of current public sector standards of care in Malawi and most SSA settings.

5.4.2 Transfusions and bleeding

- RBC transfusions can be given per treating provider discretion. Blood for transfusion is not universally available in Malawi and study treatment will not be held awaiting transfusions as anemia is a primary manifestation of MCD. For patients receiving active etoposide therapy, transfusion for a hemoglobin $<7 \text{ g/dL}$ is generally recommended. For those receiving rituximab only, transfusion is generally recommended for a hemoglobin $<6 \text{ g/dL}$, but in both scenarios provider discretion will be the primary driver for transfusion decisions.
- Platelet transfusions will be recommended for platelet count $<20,000/\mu\text{L}$, or $<50,000/\mu\text{L}$ with bleeding or per treating provider discretion.

- Tranexamic acid will be recommended for bleeding and platelet count <50,000/ µl, or per treating provider discretion, when available locally. The standard dose is 1300 mg PO three times daily for the duration of bleeding episode and 24 hours after bleeding stops.

5.4.3 Anti-infective prophylaxis

- HIV-infected individuals will receive daily cotrimoxazole throughout treatment per Malawi national HIV treatment guidelines

5.4.4 Antiretroviral therapy

Antiretroviral therapy (ART) is not prescribed by the study protocol and, according to Malawi national guidelines, is left to the discretion of treating HIV clinicians. Study clinicians will collaborate with HIV clinicians to ensure receipt of ART concurrently with chemotherapy. Zidovudine-based treatment will be strongly discouraged to avoid additional myelosuppression.

5.4.5 Infections

Febrile neutropenia to be treated per UNC Project Malawi febrile neutropenia standard operating protocol (SOP) (Appendix A. Febrile Neutropenia SOP).

5.4.6 Nausea and vomiting

Antiemetic prophylaxis for etoposide is per UNC Project Malawi antiemetic SOP (Appendix B. UNC Project Malawi Antiemetic SOP). American Society of Clinical Oncology (ASCO) considers etoposide a low emetogenic agent. All patients will receive the following as antiemetic prophylaxis:

- 5-HT3 antagonist
 - Granisetron 2 mg PO or 1 mg IV
 - OR Ondansetron 8 mg PO Q6 hours x 2 doses or 8 mg IV x 1 dose
- AND dexamethasone 8 mg PO or IV

5.4.7 Extravasation

If there is evidence of chemotherapy leakage or swelling during or following chemotherapy administration, local care will be provided per UNC Project Malawi extravasation SOP (Appendix C. UNC Project Malawi Extravasation SOP). The extravasation SOP is appended to this protocol and includes surgical consultation.

5.4.8 Etoposide anaphylaxis

Anaphylaxis has been reported extremely rarely during etoposide infusion. In the case of such a reaction, patients will be treated per standard hypersensitivity reaction protocol (Appendix D. UNC Project Malawi Hypersensitivity/Infusion Reaction SOP).

5.4.9 Hypersensitivity reactions from rituximab

- Patients may experience hypersensitivity reactions during infusion of rituximab. Rituximab will be administered via slowly titrated infusion as

per instructions in section 5.2 to minimize the risk of hypersensitivity reactions.

- If hypersensitivity symptoms occur during rituximab infusion, the infusion will be stopped, and a local study investigator will be notified to evaluate the patient immediately. For patients receiving their first rituximab infusion, a local study investigator will directly supervise the entire infusion until completion.
- Initial suggested management of hypersensitivity symptoms is based on severity per Appendix D. UNC Project Malawi Hypersensitivity/Infusion Reaction SOP. Other treatments and resuscitation will be administered as clinically indicated.
- If hypersensitivity symptoms occur during rituximab infusion, the patient will be observed for at least two hours after completion of the infusion, and until all symptoms resolve. If symptoms persist without resolution for more than two hours after the infusion, the patient will be admitted to the hospital for continued observation.

5.5 Prohibited Medications/Treatments

Systemic therapies for other active malignancies or active infections.

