4.1 Inclusion Criteria

- 4.1.1** Newly diagnosed or previously treated subjects with KSHV-associated MCD that is pathologically confirmed by characteristic histologic features and latency-associated nuclear antigen (LANA) positivity by IHC.
- 4.1.2** Age ≥ 18 at time of consent.
- 4.1.3** Can provide informed consent.
- 4.1.4** HIV-infected or HIV-uninfected.
- 4.1.5** If HIV-infected, must be on or willing to start antiretroviral therapy including lamivudine or tenofovir.
- 4.1.6** Willing to comply with study visits.
- 4.1.7** MCD treatment indicated based on the presence of a symptomatic MCD flare, defined as the presence of each of the following three criteria:
 - 1. Fever (subjective or objective)
 - 2. Lymphadenopathy or hepatosplenomegaly
 - 3. At least one of the following signs or symptoms attributable to MCD by the local study investigator:
 - Weight loss $>5\%$
 - Malaise
 - Anemia (Hemoglobin <10 g/dL) within the past 4 weeks
 - Thrombocytopenia (Platelets $<100 \times 10^3/\mu\text{L}$)
 - Note that if only two of the three criteria are present, but the provider feels treatment is indicated for a symptomatic MCD flare, this will be allowed after communication with the study principle investigator (PI).
 - Note that subjects with low hemoglobin within the past 4 weeks that have since received a blood transfusion are still eligible for participation. The subject's

pre-transfusion hemoglobin value will be considered when determining risk classification.

4.1.8 Females of childbearing potential must have a negative urine pregnancy test within three days prior to registration.

- Note that females are considered of childbearing potential unless they are surgically sterile (have undergone a hysterectomy, bilateral tubal ligation, or bilateral oophorectomy) or they are naturally postmenopausal for at least 12 consecutive months. Documentation of postmenopausal status must be provided.

4.1.9 Females must agree to abstain from breast-feeding during therapy and for 6 months after the completion of therapy.

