10.5 Secondary Objectives

10.5.1 To better characterize MCD presentation in Malawi.

Basic demographics and baseline laboratory values will be summarized using descriptive statistics (i.e., means, medians, and variability measures for continuous variable; rates and proportions for binary variables).

10.5.2 To describe the efficacy of the risk-adjusted approach as determined by clinical and radiologic response rates, 90-day, one-year, and two-year EFS and OS.

An event for EFS is either relapse (defined as “MCD attack” in the Inclusion Criteria (section 4.1)), refractory disease, lost-to-follow-up (LTFU), or death. We will consider patients LTFU if they cannot be contacted by phone for three months. Given the high mortality associated with MCD and previously published literature supporting a strong association between LTFU and mortality in SSA, we will consider LTFU as a failure event for both EFS and OS.⁴³ Relapse for purposes of this study will be defined as recurrence of an “MCD attack” (Inclusion Criteria; section 4.1) requiring re-initiation of treatment, with a strong preference for biopsy-proven recurrence whenever possible. We will conduct survival analysis using Kaplan-Meier methods. Radiologic response will be assessed in parallel with clinical response with response criteria defined in section 7.1.7. We will assess the prognostic value of radiologic response for EFS and OS in Cox proportional hazards model.^{10,15,16}

10.5.3 To describe the safety, as determined by the rate of all AEs during a risk-adjusted approach to treatment of MCD in Malawi.

All AEs will be described up to 30 days after final dose of MCD-directed treatment.

10.5.4 To describe the rate of KS exacerbation, as defined by symptomatic or clinical (dermatologic or visceral organ) exacerbation of disease.

The rate of KS exacerbation will be reported as the number of KS cases requiring KS-specific treatment divided by the number of patients with pre-existing KS (as defined by personal history of KS, baseline presence of KS, or KS in lymph node biopsy). This will be estimated along with a 95% confidence interval for the proportion.

10.5.5 To describe the quality of life of patients with MCD before, during and after treatment with a rituximab-based, risk-adjusted treatment approach, as assessed by the MCD symptom score⁴² and PROPr instrument.⁴⁴

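### Section 5.5 bans systemic treatment of active infections without exception or period, which contradicts the protocol's own infection management in 5.4.5, Appendix A and 6.1.6

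*Combined protocol and SAP*

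**What the plan says.** The full text of Section 5.5 is "Systemic therapies for other active malignancies or active infections". The Amendment 1 summary lists it as a deliberate therapeutic change.

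Other sections bear on the same treatments:

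- Section 5.4.5, under a heading that marks its contents as allowed: "Febrile neutropenia to be treated per UNC Project Malawi febrile neutropenia standard operating protocol". Appendix A then sets out oral and intravenous antibiotic regimens, with escalation and possible antifungal therapy.
- Section 6.1.6, in the paragraph on hepatitis B, expects antiviral therapy to be started in patients who develop viral hepatitis.
- Section 4.1.4 admits patients who are "HIV-infected or HIV-uninfected", and 4.1.5 adds: "If HIV-infected, must be on or willing to start antiretroviral therapy including lamivudine or tenofovir". Section 5.4.4 lists antiretroviral therapy (ART) among the allowed treatments.
- Section 4.2 uses nearly the same terms as 5.5 for its exclusions: "Second active malignancy requiring systemic therapy" (4.2.3) and "Active infection requiring systemic therapy" (4.2.5).
- Section 10.5.4 takes as the numerator of the KS exacerbation rate "the number of KS cases requiring KS-specific treatment".

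**The concern.** A prohibition and a directive cover the same treatment, and nothing says which prevails. Infection on study is foreseeable: Section 1.3 cites a high burden of opportunistic infection in the region and more treatment-related infections when rituximab was added to chemotherapy in HIV-infected patients with low CD4 counts. Section 11.4 allows departures from the protocol only in emergencies.

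Patient care is the first thing at stake, since it depends on which section staff follow. The second is the primary endpoint (Section 3.1), which counts non-hematologic events of Grade 3 or above through twelve weeks. Section 10.2 rejects the 40% null at 6 or fewer events in 24 patients, so a seventh event changes the conclusion. If early infections are handled differently from patient to patient, the number reaching Grade 3 could differ too. Section 10 also does not say how patients who receive a prohibited therapy are handled in the analysis.

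**Working it through.** **The plan's own figures.** Section 10.2 gives 24 evaluable patients, rejection at 6 or fewer events, null rate 40%, expected rate 20%, one-sided exact test at 0.1.

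- Attained alpha: P(X ≤ 6 | n = 24, p = 0.40) = 0.096, within 0.10.
- Power: P(X ≤ 6 | n = 24, p = 0.20) = 0.811, against the stated 80%.
- Enrolment: 24 / (1 − 0.10) = 26.7, rounded up to 27.

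All three reproduce, and none takes anything from Section 5.5 as an input.

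**The passages side by side.**

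| Situation on study | Section 5.5 read literally | Elsewhere | Result |
|---|---|---|---|
| Febrile neutropenia | Systemic treatment prohibited | 5.4.5 and Appendix A direct oral or IV antibiotics | Contradiction |
| Viral hepatitis on rituximab | Prohibited | 6.1.6 foresees antiviral therapy | Contradiction |
| Other infection, not neutropenic, not an emergency | Prohibited | 5.4 is silent | Only the ban applies |
| Emergency or immediate hazard | Prohibited | 11.4 and 11.4.1 permit departure | Covered by the emergency clauses |
| Cotrimoxazole in HIV-infected patients | Not clearly caught, being prophylaxis | 5.4.3 provides for it | No clear conflict |
| ART | Caught only if HIV on ART is an active infection | 4.1.5 requires it, 5.4.4 allows it | See next step |
| KS exacerbation | Systemic therapy prohibited | 10.5.4 counts cases requiring KS-specific treatment | Conditional, see below |

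**ART.** Section 4.2.5 excludes an active infection that requires systemic therapy. If HIV on ART counted as one, 4.2.5 would exclude the patients whom 4.1.4 and 4.1.5 admit, and for whom they require ART. Section 5.5 uses the same term, so the consistent reading is that HIV on ART is outside it.

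**KS.** Section 3.2.7 defines exacerbation by symptoms or clinical evidence, with no treatment needed. Section 10.5.4 counts cases that require KS-specific treatment. It does not say that the treatment must be systemic, must have been given, or must fall within study therapy. The two sections collide with 5.5 only when an exacerbation needs systemic therapy during the unstated period that 5.5 covers.

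**Size.** Section 1.2 gives two HIV shares among MCD cases: 83% in a French cohort, and 25 of 25 in the sponsor's cohort (the same 25 cases appear in 25/360 overall and 25/189 among the HIV-infected). The exact 95% lower limit for 25/25 is 0.025^(1/25) = 0.863. Applied to 27 enrolled:

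- 27 × 0.83 = 22.4
- 27 × 0.863 = 23.3
- 27 × 1.00 = 27

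This range of about 22 to 27 would count breaches only on the ART reading rejected above. On the supported reading, those affected are the participants treated for an on-study infection, plus any who need systemic KS therapy while 5.5 applies. The documents give no rate for that group, so no figure follows.

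**The case against.** The best defence is that a specific permission qualifies a general ban. Febrile neutropenia has its own allowed section and a full operating procedure, placed shortly before 5.5. Emergencies are covered by 11.4 and 11.4.1. Section 5.7 lets study treatment stop for intercurrent illness, and 5.9 then leaves further therapy to the treating provider. This softens the conflict without removing it. Section 5.5 does not defer to 5.4, and an infection that is neither neutropenic nor an emergency has no matching permission, apart from the viral hepatitis text in 6.1.6.

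The defence also says that the analysis is largely protected already. Sections 5.3 and 8.3 make treated patients evaluable for toxicity, 5.8 keeps all subjects in follow-up, and 8.4 does not remove anyone from efficacy for receiving a prohibited therapy. That stands, so the analysis change is a confirmation and does not repair a shown bias.

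Three stronger readings are tempting, and the documents support none of them:

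- A reader might infer that nearly every participant breaches 5.5 through ART. Sections 4.1.4, 4.1.5, 4.2.5 and 5.4.4 together show that this is not the protocol's usage.
- A reader might infer that obeying 5.5 pushes the KS rate toward zero. A case that requires treatment is counted under 10.5.4 even if treatment is withheld, and the treatment need not be systemic.
- A reader might infer that treating an infection is a protocol violation. Section 11.4.3 reserves that term for variances involving harm or added risk, damage to scientific integrity, misconduct, or serious or continuing noncompliance. Treatment under the protocol's own procedure does not plainly meet any of these.

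**Conclusion.** The contradiction is real and limited in scope. As written, Section 5.5 conflicts directly with 5.4.5, Appendix A and 6.1.6, and it leaves other non-emergency infections under the ban alone. For KS the conflict is conditional.

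No effect on a planned estimate can be quantified, and its direction is not known. That Grade 3 counts could shift rests on an assumption: that staff would resolve the conflict differently from case to case. The design figures in Section 10.2 stand. The point still merits an amendment, because it concerns care during a foreseeable event that can count in the primary endpoint. Which clinical rule is right is not judged here.

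**What to change.** - Reconcile 5.5 with 5.4.4, 5.4.5, Appendix A and the hepatitis text in 6.1.6, so that a single rule applies to infections arising on study, including those that are neither neutropenic nor emergencies. The choice of rule is a clinical decision for the sponsor.
- State the period that 5.5 covers and how it relates to the KS-specific treatment counted in 10.5.4.
- Confirm in Section 10 that patients who receive systemic therapy for an infection or another malignancy stay in the safety, EFS, OS and KS analyses.

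The cost is amendment wording, with no change to sample size, alpha or power.
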